### 14.1 Performance Goals

#### 14.1.1 Performance Goal: Primary Effectiveness Endpoint

The primary effectiveness performance goal endpoint in the study is primary patency. The statistical hypothesis on this endpoint is that primary patency through 12 months will exceed a performance goal established from historical literature references using venous stenting as the treatment of choice. Formally, the null and alternative hypotheses to be tested appear below:

$$H_0: \pi \leq PG$$

$$H_A: \pi > PG$$

Where  $\pi$  is the primary patency at 12 months in the study population and PG is the performance goal, which is calculated as follows. An extensive and independent review of the available literature produced references on venous stenting in similar patient populations. These data are derived from published studies of venous stenting which measured target vessel patency as an endpoint. In order to estimate the expected rate of primary patency in the study population at 12 months, the review of the available literature was used (see Appendix A Scientific Literature Search).

Based on the literature, the weighted mean expected primary patency was 85.7%. By subtracting a margin of indifference of 10% from expected performance (85.7% - 10% = 75.7%); consequently, the value of 75% is therefore taken as the performance goal for the current study.

For analysis of the imaging component of primary patency, if a subject has both a valid venogram and DUS during the 12-month follow-up period then the venogram will be used. If no venogram is available, then the DUS will be used.

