## Effectiveness Outcomes

The effectiveness outcomes of the publications comprised technical success and patency rates; primary, primary-assisted and secondary. Technical success at the time of the index procedure was defined differently from study to study. In general, technical success implied successful delivery and deployment of the stent at the intended location without significant residual stenosis. Primary patency was defined as the absence of occlusion or target lesion reintervention. Primary-assisted patency was defined as the absence of occlusion irrespective of whether TLR was performed. Secondary patency was defined when the target lesion was patent irrespective of reintervention, as long as patency was restored. Duplex ultrasound was the most common post-procedure imaging surveillance modality utilized, but many studies also employed contrast venography in follow-up.

Technical success at the index procedure was 95.8% and was highest in non-thrombotic cases (98.8%) and lowest in post-thrombotic cases (92.0%). The primary patency rate for venous stenting was 85.7% at one year (**Table XIII**). Reintervention was often successful when stent stenosis or occlusion occurred, with primary-assisted and secondary patency rates of 93.8% and 95.2%, respectively. Patency rates were highest in patients with non-thrombotic disease (12-month primary patency 94.8%) and lowest in post-thrombotic patients (12-month primary patency 80.5%).

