Stent migration	
Stent migration (as part of primary safety and secondary MAE endpoints): position change of a properly sized venous stent observed with an imaging modality, with displacement of the stent outside of the intended treatment segment after the conclusion of the index procedure, as determined with regard to a reference anatomic structure.
 
Delayed stent migration (as part of secondary endpoint): position change of a venous stent observed with an imaging modality > 1 cm from its original location at the conclusion of the index procedure, as determined with regard to a reference anatomic structure.
 
Stent migration occurs following the proper deployment of a venous stent after the index procedure (i.e. stent movement or dislodgement during the index procedure will not be noted as stent migration).

Stent thrombosis	
Occlusion of the stented venous segment occurring at any time following stent placement.
 
Stent thrombosis may be diagnosed by Duplex Ultrasound. It needs to be confirmed by venogram or IVUS.

Thrombosis	
A total occlusion due to thrombus formation as confirmed by sudden onset of symptoms and documented by DUS and venogram and/or IVUS at the target vessel.

Vein compression syndrome	
A condition in which compression of the common iliac venous outflow tract of the left lower extremity may cause discomfort, swelling, pain, or blood clots

	(deep vein thrombosis) in the iliofemoral vein (also known as the May-Thurner syndrome).
Venous occlusive disease	Any pathologic process that occurs from underlying stenosis or occlusion of the veins.

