**Late success secondary endpoints**

- 4. Primary Assisted Patency at 12 months:** Uninterrupted patency of the stented segment of the target lesion with a secondary intervention, also known as an adjunctive treatment (e.g. balloon venoplasty, subsequent stenting, etc.).
- 5. Secondary Patency at 12 months:** Patency of the stented segment of the target lesion after subsequent intervention for an occlusion.
- 6. Target Lesion Revascularization (TLR) through 30 days, 6-, 12-, 24- and 36 months:** Any reintervention of the stented segment of the target lesion.
- 7. Major Adverse Events (MAE) through 6-, 12-, 24- and 36 months:** MAEs include:
  - All-cause death occurring post-procedure
  - Clinically significant (i.e. symptomatic, confirmed by CT pulmonary angiography) pulmonary embolism
  - Major bleeding complication (post-procedural)
  - Stent thrombosis confirmed by imaging as assessed by core laboratory
  - Stent migration confirmed by imaging as assessed by core laboratoryNote: Migration excludes stent dislodgement at the index procedure as may occur with undersizing of a stent  
All MAEs will be adjudicated by a CEC, except for stent thrombosis and stent migration as they are confirmed by core laboratory.
- 8. Delayed Stent Migration at 12-, 24-, and 36 months:** position change of a venous stent observed with an imaging modality > 1 cm from its original location at the conclusion of the index procedure, as determined with regard to a reference anatomic structure.
- 9. Stent Fracture at 30 days, 12-, 24- and 36 months:**  
Fracture or breakage of any portion of the stent.  
Determined by X-ray for the first 30 subjects at 30 days and for all subjects (including the first 30 subjects) at 12-, 24- and 36 months using the following classifications (36) as adjudicated by a venous stent fracture core laboratory:
  - i. Type 0 – No strut fractures
  - ii. Type I – Single tine fracture
  - iii. Type II – Multiple tine fractures
  - iv. Type III – Stent fracture(s) with preserved alignment of the components
  - v. Type IV – Stent fracture(s) with mal-alignment of the components
  - vi. Type V – Stent fracture(s) in a trans-axial spiral configuration
- 10. Change in VEINES-QOL/Sym Score at 6-, 12-, 24- and 36 months:** Defined as the change in VEINES-QOL/Sym score at 6, 12, 24, and 36 months compared to baseline.

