1. CD-TLR
2. Imaging endpoint of Occlusion/Restenosis

Primary patency endpoint determination will follow the rules described below:

1. Censor any imaging assessments or events after any TVR (not clinically driven) as this changes the vessel making the subject unevaluable for patency at 12 months. If the date of assessment > date of TVR, then set the value to 'missing'
2. All Subjects that had CD-TLRs within 390 days will be counted as Primary Patency Failure whether or not an imaging assessment is available after the CD-TLR event. Subjects with TVR (not clinically driven) before the CD-TLR will be censored.
3. The imaging component of the 12-month primary patency will be constructed based on 'AT' principle – prior events will not be carried over to a later visit. For each subject, qualified imaging assessment will be determined in the following order:
  - a. Venogram on scheduled 12-month visit regardless of window.
  - b. DUS on scheduled 12-month visit regardless of window
  - c. Venogram from unscheduled visit within the imaging window, choose the one closest to the target visit date if there are multiple
  - d. DUS on unscheduled visit within the imaging window, choose the one closest to the target visit date if there are multiple

Primary Patency at 24 months, and 36 months follow-up will be determined following the similar convention specified above for 12 months.

For each individual component of the primary patency endpoint, the rate will be calculated in the following way:

The proportion rate of CD-TLR will be constructed as a clinical/safety endpoint - number of subjects with CD-TLR over number of evaluable subjects through the cutoff of a reporting time point. For example, for 12-month CD-TLR under the primary patency endpoint, the cutoff to determine the numerator is 390 days – this includes any subjects who had their first CD-TLR within 390 days. The denominator will be all subjects that had CD-TLR or had no CD-TLR but had at least 330 days of clinical follow-up.

The CD-TLR Endpoint will be reported cumulatively.

The determination of imaging component of the occlusion/restenosis endpoint is described above.

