**Table 5. Primary Assisted Patency and Secondary Patency Endpoints**

Outcome Scenarios	Primary Patency	Primary Assisted Patency	Secondary Patency
Patent (DUS, Venogram) at 12 months, no CD-TLR and no TLR before 12 months	Success	Success	Success
Binary Restenosis/Occluded (DUS, Venogram) at 12 months, and no TLR (not clinically driven) before 12 months	Failure	Failure	Failure
TLR (not clinically driven) before 12 months, before any CD-TLR , before 12 month imaging	Missing	Missing	Missing
Patent Venogram, DUS) at 12 months, CD-TLR before 12 months due to restenosis but no occlusion	Failure	Success	Success
Patent (Venogram, DUS) at 12 months, CD-TLR before 12 months due to occlusion	Failure	Failure	Success
Image missing at 12 months, CD-TLR before 12 months due to restenosis but no occlusion	Failure	Missing	Missing
Image missing at 12 months, CD-TLR before 12 months due to occlusion	Failure	Failure	Missing

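### SAP Table 5 scores a stent that occluded and later reopened without revascularization as a primary-assisted patency success, against that endpoint's own definition, and the supportive Kaplan-Meier analysis does not say how to treat such an occlusion

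*SAP*

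**What the plan says.** **Scoring rule.** SAP 10.3.2.2 builds the imaging part of 12-month primary patency from one qualifying image at the visit, and "prior events will not be carried over to a later visit". The interim event that makes a subject a failure is a clinically driven revascularization: "All Subjects that had CD-TLRs within 390 days will be counted as Primary Patency Failure whether or not an imaging assessment is available". The 24- and 36-month visits follow a similar convention.

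**Table 5.** Row 1 reads "Patent (DUS, Venogram) at 12 months, no CD-TLR and no TLR before 12 months" and gives success in all three patency columns. It sets no condition on earlier imaging.

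**Primary-assisted patency.** SAP 7.9.3, item 4, defines it as "Uninterrupted patency of the stented segment of the target lesion with a secondary intervention". Protocol 6.3.2 and Appendix B use the same definition, and Protocol 6.3.2 now asks for it at 24 and 36 months as well.

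**Primary patency.** Protocol 6.3.1 and SAP 7.9.1 define it *at* 12 months. Protocol 14.1.1 introduces the test with "The statistical hypothesis on this endpoint is that primary patency through 12 months will exceed a performance goal", but the parameter it then defines is patency *at* 12 months.

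**Benchmark.** In Protocol Appendix A, Effectiveness Outcomes, "Primary patency was defined as the absence of occlusion or target lesion reintervention". Assisted patency there meant no occlusion, whether or not the lesion was revascularized.

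**Supportive analysis.** SAP 7.9.1.2 plans Kaplan-Meier estimates of primary patency through 360 and 390 days. It does not say whether an occlusion seen on an interim image is an event.

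**The concern.** Duplex ultrasound is scheduled at discharge, 30 days and 6 months (Protocol Table 7) and is read by the core laboratory, so an occlusion before 12 months can be seen. If that stent is open again at 12 months and no revascularization took place, row 1 applies and the interim occlusion disappears from all three patency rates.

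For primary-assisted patency, an occluded stent has not been uninterrupted in its patency, so the table and the definition give opposite answers. For primary patency the conflict is weaker: the rule fits the trial's wording but differs from the stated definition behind the 75% goal. The one planned analysis that could show the difference leaves the relevant event undefined. At stake are a descriptive secondary endpoint at three visits and the clarity of the supportive comparison with 75%.

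**Working it through.** **1. Follow one stent that is patent on the 12-month image.**

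| Before 12 months | Table 5 row | Primary | Assisted | Secondary |
|---|---|---|---|---|
| Never occluded, no revascularization | 1 | Success | Success | Success |
| Occluded on an earlier image, reopened, no revascularization | 1 | Success | Success | Success |
| Clinically driven revascularization for restenosis, no occlusion | 4 | Failure | Success | Success |
| Clinically driven revascularization for occlusion | 5 | Failure | Failure | Success |
| Revascularization not clinically driven, before the image | 3 | Missing | Missing | Missing |

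Rows 4 and 5 differ only in whether there was an occlusion, and only the assisted column changes. Occlusion is therefore what ends assisted patency in the SAP's own table. Row 1 does not apply that criterion, so the second line above is inconsistent with row 5 and with the definition.

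**2. Do other planned analyses pick it up?**
- Multiple imputation and tipping point (SAP 7.4) deal with missing outcomes. This subject is not missing.
- The Kaplan-Meier analysis leaves the event undefined.
- Stent thrombosis in the safety composite is "Occlusion of the stented venous segment occurring at any time following stent placement", but Appendix B requires confirmation by venogram or IVUS. During follow-up before 12 months a venogram is mandatory only at re-intervention (Protocol 10.12.6.1). An ultrasound-only occlusion may therefore be missed there too.

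**3. Reproduce the plan's figure.** Inputs from SAP 6.3: N = 160, goal 0.75, expected rate 0.857, reject at 131 or more. Exact binomial:
- P(X ≥ 131 | 0.75) = 0.0247
- P(X ≥ 131 | 0.857) = 0.9288

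Both match the SAP, and 131/160 = 81.9%. The arithmetic of the plan is sound.

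**4. Weight of one subject.** 1/160 = 0.625 percentage points.

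**5. How many subjects?** The documents do not say. The only related figure is the literature 30-day stent thrombosis rate of 2.9% (Appendix A, Table XI, counted per limb):
- 0.029 × 160 = 4.6
- 0.029 × 200 = 5.8

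As an assumption, early events give a range of 0 to about 5 of 160, or 0 to about 6 of 200. The top of the range needs every such stent to reopen without revascularization and be patent at 12 months, which nothing in the documents supports. No rate is given for later occlusions that reopen.

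**6. Effect on the primary comparison.** 0.857 × 160 = 137.1, so take 137/160. Its exact one-sided 97.5% lower limit is 79.2%.
- *If 85.7% follows the literature definition*, occlusions are already failures in it. The carry-forward expectation is 137, and the at-visit rule can only add to it, up to about 137 + 5 = 142 (88.8%). Subtracting thromboses from 137 would count them twice.
- *If 85.7% is instead taken as the at-visit rate*, removing 5 gives 132/160 (lower limit 75.7%) and removing 6 gives 131/160 (75.02%). Both pass. It takes 7 (130/160, 74.3%) to fail, which is beyond the early-event range.

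Neither reading shows a crossing of the goal.

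**The case against.** The strongest reply is that the at-visit rule is the stated endpoint. The definition and the tested parameter both say *at* 12 months, and the rule was pre-specified. Calling the hypothesis a contradiction because one sentence says *through* would be selective. That stands, and it is why the primary test should be left alone.

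A reader might infer that the investigator's choice of rescue decides the patency result. The documents do not support that. The clinical events committee adjudicates whether a revascularization was clinically driven, using core-laboratory imaging. A stent still occluded at 12 months fails whatever was tried, and reopening may be spontaneous. Protocol Table 12 does list anticoagulation for venous occlusion or thrombosis, but it covers events inside or outside the stented segment and lists procedures as well. Anticoagulation is also already recommended after stenting, so it is not shown to be a separate choice.

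It is also fair to say that a confirmed early occlusion is not hidden: it counts in the 30-day safety endpoint, and study success needs both endpoints. The difference from the benchmark also runs both ways, since the trial fails subjects for restenosis of 50% or more, which the literature definition does not mention. Finally, assisted patency is a secondary endpoint with no inference planned.

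These points limit the consequence. They do not reconcile row 1 with the assisted-patency definition, and they do not settle what the Kaplan-Meier event is.

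**Conclusion.** The inconsistency in primary-assisted patency is established from the text and needs no assumption about frequency: row 1 of Table 5 gives a success where the definition and row 5 require a failure. For primary patency the rule is legitimate. What is missing is a defined event for the supportive time-to-event analysis, which matters because the benchmark's stated definition treats occlusion as loss of patency.

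The size is unknown and may be zero. Each affected subject is about 0.6 percentage points of 160. Taken alone, the row 1 rule can only raise the assisted rate, and can only raise the primary rate relative to a carry-forward count. A reader might infer that the primary result could be tipped across 75%. The documents give no basis for that: the frequency is not stated, the expected 85.7% already excludes occlusions on the literature's definition, and even six reclassified subjects leave 131/160, which passes.

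**What to change.** 1. **Add one row to Table 5:** core-laboratory occlusion before the visit, patent at the visit, no revascularization. Score primary-assisted patency as failure and secondary patency as success, and apply it at 12, 24 and 36 months. Under the unchanged at-visit rule the primary column stays success, so a footnote should say that primary patency is scored at the visit and assisted patency over the whole interval.
2. **Leave the primary test unchanged, and define the Kaplan-Meier event in SAP 7.9.1.2** to include any core-laboratory occlusion from the index procedure onward, however it was treated. Report the number of affected subjects and the 12-month rate with its lower limit beside 75%. Show venogram- or IVUS-confirmed occlusions separately from ultrasound-only ones, because confirmation before 12 months is mandatory only at re-intervention.

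**Cost:** SAP wording and one further run on images that the core laboratories already read. The assisted and supportive rates may come out slightly lower.

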## 10.11 Unscheduled Visits

Unscheduled visits are additional non-scheduled visits that occur at times other than the predetermined intervals and during which an intervention in the target vein takes place. If the Abre stent(s) is(are) explanted, the subject will be followed for safety reporting only for 30 days post-explant. AE data should be collected on the AE eCRF, and study exit data should be collected on the Study Exit eCRF. It is not allowed to implant a new Abre stent during the reintervention. The following assessments will be completed and the data will be recorded on the Follow-up eCRF:

- Physical assessment of limbs
- Villalta Score and VCSS (for both limbs, should be taken before any intervention)
- Quality of Life Questionnaires: EQ-5D and VEINES-QOL/Sym (should be taken before any intervention)
- INR for subjects on warfarin
- Duplex ultrasound (target limb)
- Duplex ultrasound (contralateral limb); image of the CFV waveform only.
- Venogram (target limb)
- IVUS (target limb)
- Plain X-ray (target limb) is required pre and post re-intervention to assess for stent fracture

- Secondary procedure data
- Adverse events/device deficiency
- Medications: Antithrombotics, Antibiotics, Immunosuppressants, NSAIDs, Steroids, Diuretics, Calcium-channel blockers, Statins
- Discontinuation information (in case the subject ends involvement in the study)

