## 6.3 Sample Size Calculation

Primary Effectiveness: Using the assumptions above on the  $PG$  and anticipated outcome, we assume desired power of at least 92% under hypothesis testing relative to the performance goal at a one-sided alpha of 0.025. The resulting evaluable sample size required is then 160 subjects using exact binomial

test for a single proportion. Accounting for attrition during follow-up, the sample size is augmented by 20% to 200 subjects. Every effort will be made, however, to minimize loss to follow-up.

Primary Safety: Using the assumptions above on the performance goal and anticipated outcome, we assume desired power of at least 92% under hypothesis testing relative to the PG at a one-sided alpha of 0.025. The resulting evaluable sample size required is then 193 subjects using exact binomial test for a single proportion. Accounting for attrition during follow-up, the sample size is augmented by 3.5% to 200 subjects. Every effort will be made, however, to minimize loss to follow-up.

In summary, the overall power of the study is at least 84% while the effectiveness and safety PGs and the projected rates needed to achieve them are as follows:

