### 7.9.1.1 Hypothesis Testing

The primary effectiveness endpoint in this study is primary patency rate. The statistical hypothesis on this endpoint is that primary patency through 12 months will exceed a performance goal established from historical literature references using venous stenting as the treatment of choice. Formally, the null and alternative hypotheses to be tested appear below:

$$H_0: \pi \leq PG$$

$$H_A: \pi > PG$$

where  $\pi$  is the primary patency rate at 12 months in the study population and PG is the performance goal of 75%.

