### 7.9.1.2 Statistical Method

The primary patency rate is calculated as the number of subjects without loss of primary patency divided by the number of subjects having evaluable primary endpoint data for primary patency rate at 12 months.

Based on the literature (see ABRE CIP Appendix A Scientific Literature Search), the weighted mean expected primary patency was 85.7%. By subtracting a margin of indifference of 10% from expected performance ( $85.7\% - 10\% = 75.7\%$ ); consequently, the value of 75% is therefore taken as the performance goal for the current study. The 12-month patency rate and lower limit of the 97.5% one-sided confidence interval will be reported. The primary effectiveness objective will be met if the lower limit of the 97.5% one-sided confidence interval of the 12-month patency rate is above 75%.

For the primary effectiveness endpoint, subjects will be included in the analysis and considered evaluable if:

- (a) the subject experiences at least one clinically-driven target lesion revascularization within 390 days;
- or (b) the subject has occlusion or restenosis  $\geq 50\%$  of the stented segment of the target lesion confirmed by core laboratory at 12 months or
- (c) the subject has at least 330 days follow up without an event in the primary effectiveness endpoint.

For analysis of the imaging component of primary patency, if a subject has both a valid venogram and DUS during the 12-month follow-up period then the venogram will be used. If no venogram is available,

then the DUS will be used. This is an imaging endpoint. More details of the reporting rules are used to determine this endpoint can be found in section 10.3.2.

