Further, as supportive analysis on the primary endpoints, time-to-event analysis for primary patency through 12 months will also be performed and serves as a secondary analysis. Kaplan-Meier (KM) estimates with 95% two-sided confidence interval using Peto formula will be reported for primary patency rate through 360 days as well as 390 days to accommodate the 12-month visit window. Subjects not experiencing the event by 12 months will be censored at 12 months or last known follow-up as defined in Appendix A, whichever is earlier. Subjects not experiencing the CD-TLR but experiencing the Target Vessel Revascularization (TVR) before 12-month imaging window will be censored at date of TVR when evaluating the 12-month primary effectiveness endpoint. The imaging assessment for such subjects that are available either on or before the TVR date, if within the 12-month reporting window, may still be used.

Sensitivity analyses for primary effectiveness endpoint include multiple imputation and tipping point analysis which are further explained in section 7.4.

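### A stent documented as occluded or at least 50% restenosed before day 271, then re-treated before day 271 without symptoms, is scored Missing rather than Failure for 12-month primary patency

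*SAP*

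**What the plan says.** Primary patency requires freedom from occlusion, from restenosis of 50% or more, and from clinically driven TLR at 12 months (Protocol 6.3.1; SAP 7.9.1). A revascularization is clinically driven only if baseline symptoms recur or new ones appear.

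SAP 10.3.2.2 then sets three rules:
- **Rule 1.** Images and events after a TVR that is not clinically driven are set to missing, because the intervention alters the vessel and the subject can no longer be assessed for patency at 12 months.
- **Rule 2.** A CD-TLR within 390 days is a Failure whether or not later imaging exists.
- **Rule 3.** The imaging component is taken at 12 months, and "prior events will not be carried over to a later visit". It accepts scheduled 12-month images, or unscheduled images inside the Table 4 window of day 271 to 420.

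SAP Table 5, row 3, covers "TLR (not clinically driven) before 12 months, before any CD-TLR , before 12 month imaging" and scores it Missing for all three patency endpoints. SAP 7.9.1.2 divides by evaluable subjects only. In the Kaplan-Meier analysis it censors at the TVR date and adds that an image on or before that date, "if within the 12-month reporting window, may still be used".

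The earlier images exist. Protocol 10.12.6.2 has DUS assess patency at 6 months. Protocol 10.11 requires DUS, venogram and IVUS at an unscheduled visit "during which an intervention in the target vein takes place". Core laboratories read all of these.

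**The concern.** Re-treatment of a stented segment usually follows a finding that the segment has narrowed or closed. When that finding is already documented by the core laboratory, the outcome is known. Scoring it Missing because the stent was re-opened removes a known loss from the denominator, and removes it because of the loss. Compared with scoring it Failure, this can only raise the observed patency rate.

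The tested rate decides whether the effectiveness goal is met, so a rule that moves known losses out of it matters even if few subjects are involved. The same convention governs patency at 24 and 36 months.

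**Working it through.** **1. Five courses under the rules**

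| Course | Governing text | 12-month score |
|---|---|---|
| A. Loss seen at month 6, not re-treated, still present at 12 months | Rule 3; Table 5 row 2 | Failure |
| B. Loss seen at month 6, re-treated before day 271 for symptoms | Rule 2 | Failure |
| C. Loss seen at month 6, re-treated before day 271 without symptoms | Rules 1 and 3; Table 5 row 3 | Missing |
| D. Loss on an image from day 271 on, then re-treated without symptoms before the 12-month visit | SAP 7.9.1.2; 10.3.2.1; Table 5 row 3 | Unclear |
| E. Loss seen at month 6, not re-treated, patent at 12 months | Rule 3 | Success |

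Course C is the point. Rule 2 does not apply because there are no symptoms. Rule 1 removes every later image. Rule 3 cannot use the earlier one. No rule returns Failure. Rule 1 speaks of TVR and Table 5 of TLR, but re-treatment of the stented segment falls under both.

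Course D is ambiguous. SAP 7.9.1.2 permits a pre-TVR image inside the window, SAP 10.3.2.1 applies the window only to subjects who missed the scheduled visit, and Table 5 row 3 has no exception.

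**2. Later visits.** The Table 4 windows are day 421 to 780 (24 months) and day 781 to 1140 (36 months). By the same steps, a known failure re-treated without symptoms before day 421 can become Missing at 24 months, and one re-treated before day 781 can become Missing at 36 months.

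**3. The plan's own figure.** Inputs from SAP 6.3: N = 160, goal 0.75, expected rate 0.857, one-sided alpha 0.025, reject if R ≥ 131.
- P(X ≥ 131 | 160, 0.75) = 0.0247 and P(X ≥ 131 | 160, 0.857) = 0.9288. Both match the SAP output.
- P(X ≥ 130 | 160, 0.75) = 0.0384, so 131 is the critical value.

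**4. Putting losses back.** The exact one-sided 97.5% lower limit for x successes in n is the 0.025 quantile of Beta(x, n − x + 1). SAP 7.9.1.2 does not name the interval method for effectiveness; I use the exact one because the sample size does. Each restored loss adds 1 to n and 0 to x.

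| Start | Losses restored | x/n | Lower limit | Above 75%? |
|---|---|---|---|---|
| Minimum pass | 0 | 131/160 | 75.02% | yes |
| | 1 | 131/161 | 74.48% | no |
| | 2 | 131/162 | 73.95% | no |
| Planning rate (0.857 × 160 = 137.1) | 0 | 137/160 | 79.2% | yes |
| | 4 | 137/164 | 77.0% | yes |
| | 8 | 137/168 | 74.84% | no |

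**5. Type I error, with an assumed share q affected.** Suppose true patency is exactly 75% when these subjects count as failures. Of 160 subjects, M ~ Binomial(160, q) become Missing, and the other 160 − M succeed with probability 0.75/(1 − q). Averaging the exact test over M gives:

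| q (assumed) | 0.75/(1 − q) | One-sided type I error |
|---|---|---|
| 0% | 0.7500 | 0.0247 |
| 1% | 0.7576 | 0.033 |
| 2% | 0.7653 | 0.052 |
| 3% | 0.7732 | 0.080 |
| 5% | 0.7895 | 0.176 |

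**The case against.** **The endpoint is defined at 12 months and names only clinically driven TLR.** Not carrying findings forward follows that wording, and rule 1 gives a reason for its censoring. Part of this stands: scoring course C as Failure needs an explicit new rule, and it will sit beside course E, which stays Success. But the at-12-months principle explains ignoring an early image when a valid 12-month image exists. In course C rule 1 has removed that image, and the last valid observation is a documented loss. The hypothesis in SAP 7.9.1.1 is also worded as patency through 12 months.

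**Missing outcomes are already handled.** SAP 7.4 plans multiple imputation and a tipping-point analysis. Both are sensitivity analyses, and the imputation covariates omit the earlier core-laboratory finding, so a known loss could be imputed as patent. Evaluability criterion (c), at least 330 days of follow-up without an event, might be read as keeping the subject in. That conflicts with Table 5 and still does not give Failure.

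**The events are reported elsewhere.** True: any TLR and confirmed stent thrombosis are secondary endpoints. They are not the tested rate.

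**Stronger readings a reader might infer, which the documents do not support:**
- *A clean switch from Missing on day 270 to Failure on day 271.* Course D is unsettled, so Failure from day 271 is not established.
- *Any failure re-treated without symptoms is lost at 24 and 36 months.* Re-treatment inside a later window comes with a required venogram that may itself qualify as a failing image.
- *The trial is biased upwards against the 85.7% benchmark.* In the literature review, "Primary patency was defined as the absence of occlusion or target lesion reintervention". That is stricter than the trial on re-intervention without symptoms, but it does not list untreated restenosis of 50% or more, which the trial counts as loss. The net direction is unknown.
- *Two to four subjects are affected.* The literature TLR rate of 8.3% gives 200 × 0.083 = 16.6 re-interventions, but it is not split by symptoms, timing or prior imaging. The symptom definition is broad, which shrinks the group.

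**Conclusion.** The concern holds for core-laboratory loss before day 271 followed by re-treatment of the stented segment, also before day 271, that does not meet the clinically driven definition. Such a subject is scored Missing for 12-month primary patency and leaves the denominator, although the same lesion scores Failure when untreated and persistent or when re-treated for symptoms. From day 271 the text is ambiguous and needs settling. At 24 and 36 months the problem arises for re-treatment before day 421 and day 781 respectively; those analyses are descriptive.

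The size cannot be fixed from the documents. One subject is enough at the minimum pass; at the planning rate eight are needed, so a result near 85.7% would survive a handful. The type I error figures rest on the assumed q and on counting these losses as failures. They show sensitivity, not an estimate of what happened.

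**What to change.** Amend rule 1 of SAP 10.3.2.2 and split Table 5, row 3. When a TLR that is not clinically driven makes later imaging unusable, the last core-laboratory image on or before the TLR date decides:
- occlusion or restenosis of 50% or more of the stented segment: Failure, and in the Kaplan-Meier analysis an event at that image date instead of censoring at the TVR date;
- patent stent: Missing, as now.

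State that this applies both before and inside the day 271 to 420 window, which removes the conflict between SAP 7.9.1.2, 10.3.2.1 and Table 5.

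Use the rule for the 24- and 36-month patency analyses still to be reported. The 12-month data went into the application submitted on 27 April 2020 and approval followed in October 2020, so for that analysis report the rule as a sensitivity analysis beside the existing result, with the number of subjects it moves.

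The cost is one rule and one split table row, with no new data because the images are already required and centrally read. The downside is that the reported patency rate may be slightly lower.
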